### **14. POTENTIAL RISKS**

Risks from participation in this study may include the following:

#### Medicinal mushroom risk

Mushrooms have been widely consumed throughout the globe for hundreds of years. In China, the use of mushrooms extends back in time for millennia. Their overall tolerability in clinical settings has been documented by several research groups. Compared to most herbal products, safety research on mushroom products tends to be more robust, and many large-scale clinical trials of medicinal mushroom compounds have not revealed significant adverse events or drug-drug interactions (Sullivan, Smith, & Rowan, 2006). Eleven phase I, II, and III clinical trials in stomach, colorectal, esophageal, and breast cancer patients found immunomodulatory benefits with *Tv* treatment without significant adverse effects (Standish et al., 2008). The Host Defense product line (which will be providing the mushroom products to the study) launched in 2009 and has sold hundreds of millions of units of mushroom products. Consumer adverse event reports have been recorded in compliance with FDA regulations, and have been markedly low--0.003% for *Fo* and 0.002% for *Tv*.

In regard to purity of material, identity by HPTLC and microbiological testing is conducted on each batch of Host Defense finished products. Heavy metal (As, Pb, Hg, Cd) and pesticide (USP 561) testing is carried out on the raw material. The products are manufactured in full compliance with 21 CFR Part 111 Current Good Manufacturing Practice in Manufacturing, Packaging, Labeling, or Holding Operations for Dietary Supplements.

#### FoTv risk

Host Defense *Tv* mycelium has demonstrated immunological efficacy in preclinical and clinical research settings. A review of adverse data from Host Defense indicates that the primary adverse reaction recorded with *Tv* is gastrointestinal distress- typically nausea but also diarrhea, constipation, or bloating/gas (Torkelson et al., 2012). The lack of observed cytotoxicity in the neutral red and viral yield reduction assays conducted at the BioShield Biodefense project indicates tolerability on a basic cellular level (P. Stamets, 2014, 2015). In a separate research effort with Washington State University, agarikon has been well tolerated in honeybee populations (unpublished). No clinical safety data could be identified in the literature. Host Defense product adverse event records reveal extremely few complaints - the manufacturer has received two reports of nausea since 2016, with no other reported adverse events. From 2016 to present, more than 500,000 units of Host Defense Turkey Tail and 60,000 units of Host Defense Agarikon have been consumed, thus establishing a good safety profile for human consumption.

#### *Effects of upregulation of IL-1-β and IL-6 on COVID-19 disease progression*

Concern has been raised regarding isolated polysaccharide extracts and induction of IL-1B, an inflammatory cytokine that may exacerbate the runaway inflammatory presentations in later stages of the COVID-19 disease (Alschuler et al., 2020). Polysaccharides in mushrooms have been shown to initiate an immune response, sparking activity of TNF- $\alpha$ , IL-1B, IL-6, and other pro-inflammatory proteins involved in acute immune activation. However, other biologically active compounds in mushrooms and mycelium (such as the sterols, phenols, and other terpenoid compounds) are important for the resolution of this inflammatory response, inducing anti- inflammatory cytokines such as IL-10 and

IL-1ra (Davis et al., 2020, Davis et al. 2020 unpublished). Therefore, an unextracted whole mushroom mycelium complex impacts the immune system in a more balanced and modulatory manner.

Nevertheless, in its review of the IND application for this study, the FDA raised the following as a non-clinical hold issue regarding FoTv:

*Because FoTv may stimulate immune function, we are concerned these products may accelerate the development or exacerbate the magnitude of COVID-19, a disease that is typically associated with excessive or aberrant host immune responses (i.e., cytokine storm). Specifically, we are concerned about the in vitro finding that Fo robustly upregulates cytokines IL-1-β and IL-6 ranging from 8,000- to 145,000-fold. Please further explain this finding and how it translates clinically, particularly in the context of COVID-19 and the risk of accelerating or exacerbating disease progression.*

While IL-1-β and IL-6 upregulation effects have been observed with aqueous extracts of Fo in vitro, these findings warrant additional context and explanation for COVID-19 clinical studies. Firstly, these pro-inflammatory immune protective cytokines are being discussed in the context of monoclonal antibody treatment for COVID-19: IL-1 $\beta$ , IL-6, and TNF- $\alpha$ . Secondly, the non-overlapping, post-aqueous ethanol extraction showed a decrease in IL-1-β and IL-6, demonstrating complex and differential effects on immune system functioning. While Fo aqueous fractions increased levels of pro-inflammatory and immune activating cytokines, it also triggered robust increases in the anti-inflammatory cytokines IL-10 and IL-1ra (as did Tv). These dual and opposing effects by different fractions of Fo may suggest a ‘regulating’ effect in vivo.

Fo has triggered the expression of cytokines relevant to other facets of viral pneumonic disease. Eotaxin is involved in the inflammatory recruitment and infiltration of eosinophils and other phagocytic cells to the lung tissue. The antiviral peptides IFN- $\gamma$ , MIP-1 $\alpha$ , and MIP-1 $\beta$  are currently being discussed in the context of SARS-CoV-2 infections, and whether high or low levels are beneficial or detrimental. IL-4, also upregulated by Fo, has protective effects in influenza, SARS, and pneumonia.

In terms of predicting potentially adverse clinical responses to FoTv, we are encouraged by the lack of reported adverse effects of these products pertaining to the exacerbation of viral infection during cold & flu season, which have sold hundreds of thousands of units over the past decade. While post market adverse effects reports are not considered to be high-quality evidence, they offer additional context into overall product safety and tolerability in a consumer population.

It is also worth mentioning that these effects were observed in PBMC cells from healthy donors. The clinical effects of FoTv in COVID-19 patients are unstudied and an adverse effect may present. We have relied on the Phase 1 safety study to monitor for any adverse effects that may result from FoTv administration.

#### mQFPD risk

The modified Qing Fei Bai Du preparation is a blend of 21 total herbs. Please refer to Appendix 1.pdf which provides a detailed safety profile of each of the herbs which was completed with the help of [name]., Pharm.D., O.M.D., L.Ac. who is the author of "Chinese Medical Herbology and Pharmacology," a seminal textbook on Chinese herbal pharmacology. Each of the potentially negative herb-drug interactions listed in the document is reflected in the exclusion criteria and monitoring requirements.

As discussed above, a recent clinical trial of 98 patients using the complete 196g decoction dose of mQFPD daily for 9 days demonstrated the following adverse reactions: 4 patients developed symptoms of nausea and vomiting, 2 patients developed symptoms of dizziness, and 1 patient developed symptoms of rash. When reported as adverse reactions per total days of treatment, the incidence of adverse reactions was 0.07% (Wang 2020). By comparison, this trial will utilize an equivalent to 74.5g per day for 14 days.

1. Of note, three of the herbs in the original QFPD formulation have additional concerns that are addressed below. The herbs and concerns are addressed as follows.  
Ma Huang (Herba Ephedrae)
  - This herb has a long history of use in China as well as domestically for viral respiratory infection, part of which is attributed to the presence of ephedrine. Unfortunately, in the 1990s it became used in extracted forms as an OTC stimulant. Subsequently, the FDA restricted OTC sales to respond to

concerns of abuse potential, but it remains available to be prescribed domestically by licensed TCM practitioners.

- In consultation with the Study Team of TCM practitioners, this herb is of central medicinal value in the formula and cannot be replaced. The dosages of ephedrine used in this study will be far lower than they were in OTC extracted forms prevalent in the 1990s.
- To ensure safety, concerns regarding drug-drug interactions and adverse events are addressed in the exclusion criteria as well as our safety monitoring as described in the protocol, which includes daily blood pressure measurements for hypertensive study participants. In addition, a certificate of analysis (COA) will be produced demonstrating specific quantities of ephedrine in the Ma Huang BRM. If the total daily ephedrine contained within 12g of mQFPD capsules exceeds the recommended maximum of 150mg per 24 hours, we will notify the FDA and amend the quantity of Ma Huang in the formula as appropriate.

2. Xi Xin (Radix et Rhizoma Asari): This herb is of concern due to the possibility of improper preparations which have contained Aristolochic acid (AA). Consequently, this herb has been restricted from importation by the FDA.

- In consultation with the study's panel of TCM practitioners, this herb is also of central medicinal value and cannot be replaced.
- To ensure proper safety standards, a certificate of analysis (COA) is attached demonstrating non-detectable quantities of AA by HPLC with tandem mass spectroscopy LC/MS/MS. This analysis was conducted on the specific batch of botanical raw material to be used in final production of study material.

3. Kuan Dong Hua (Flos Farfarae) is present in the original QFPD formula being used in China. This has been substituted with Pi Pa Ye (Folium Eriobotryae) for the purpose below:

- This herb (Flos Farfarae) contains pyrrolizidine alkaloids (PA) and may be linked to liver injuries. The FDA prohibits the use of herbs that contain PA.
- In consultation with the study's panel of TCM practitioners, this herb is not of central medicinal value and can be replaced. To avoid this issue of PA, this herb has been substituted with Pi Pa Ye (Folium Eriobotryae) in the research formulation.

This substitution requires the formula be renamed with the moniker modified QFPD, or mQFPD, to reflect the substitution of Kuang Dong Hua with Pi Pa Ye.

In addition to these concerns regarding specific herbs, Chinese medicine formulations in general have had a history of containing inappropriate amounts of heavy metals in the final protocol. For this reason, both the raw herbs and the final investigational product will be extensively tested and analyzed for heavy metals, the results to be included in the COA as specified in section 8.3.

Lastly, concerns of herb identification are present in all herbal products. To address these concerns, each of the 21 herbs in the preparation will be traceable back to its original source by the supplier by chain of custody. Further, each of the 21 herbs will undergo identification verification testing to confirm herb identity, with information submitted to the FDA for final approval prior to the initiation of recruitment.

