#### Adverse reactions to QFPD

While this study's methodology including lack of a control group leaves much to be desired, their report on adverse reactions is important considering the complete 196g decoction was administered daily for 9 days, which is a substantially larger dose than that used in the present clinical trial. In the course of treatment of 98 patients, 4 patients developed symptoms of nausea and vomiting, 2 patients developed symptoms of dizziness, and 1 patient developed symptoms of rash. When reported as adverse reactions per total days of treatment, the incidence of adverse reactions was 0.07%.

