## **18. RISK/BENEFIT RATIO**

The most significant potential benefit of this study is to contribute to the possible future availability of safe and inexpensive agents for the treatment of COVID-19. This study will generate important safety data needed to subsequently evaluate the efficacy of FoTv and mQFPD in time to provide guidance for the use of these medicines during the current pandemic.

Furthermore, the collaborations formed as part of this study will provide a foundation for future studies evaluating the safety and efficacy of similar therapeutics for treatment of active COVID- 19, and the application of these therapeutics for more severe manifestations of disease.

For the study participant, FoTv or mQFPD may potentially provide direct benefit by potentially reducing the severity of their illness as measured by duration of fever, risk of hospitalization, intubation or death. Due to the high mortality associated with COVID-19, the benefits of participation in the trial outweigh the potential risks as outlined above in the background and risks sections.

The other most significant potential benefit of this study is to contribute to the possible future availability of safe and inexpensive agents for adjunctive therapy of COVID-19 vaccination.

For the study participant, FoTv may potentially provide direct benefit by potentially reducing the severity of their symptoms or improving vaccination response. Due to the high mortality associated with COVID-19 and the high concerns of vaccine hesitancy due to side effect burden, especially during upcoming public health campaigns for booster immunizations, the benefits of participation in the trial outweigh the potential risks as outlined above in the background and risks sections.

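### Does the 0.07% adverse-reaction rate quoted for the herbal formula, about 11 times lower than its own counts imply, require a change to the plan?

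*Combined protocol and SAP*

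**What the plan says.** Section 14 (Potential Risks), under the mQFPD heading, summarises "a recent clinical trial of 98 patients using the complete 196g decoction dose of mQFPD daily for 9 days". The reactions were: "4 patients developed symptoms of nausea and vomiting, 2 patients developed symptoms of dizziness, and 1 patient developed symptoms of rash". The next sentence reads: "When reported as adverse reactions per total days of treatment, the incidence of adverse reactions was 0.07", the figure being a percentage. A cited study is given as the source.

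Section 7 (Background), under the heading on adverse reactions to QFPD, gives the same counts and the same percentage, and says that "the complete 196g decoction was administered daily for 9 days". There the product is the unmodified formula, QFPD. Section 14 labels it mQFPD, although the same section explains that mQFPD is a new name for a formula with one herb replaced.

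Section 18 (Risk/Benefit Ratio) concludes that "the benefits of participation in the trial outweigh the potential risks as outlined above in the background and risks sections".

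**The concern.** A reader who takes 0.07% at face value sees a negligible risk. The same sentences report 7 reactions among 98 patients. The percentage is the only numerical adverse-reaction rate that the documents give for this formula in COVID-19. It sits in the two parts of the protocol to which the risk/benefit conclusion refers, and safety of mQFPD is a primary objective of sub-study 1b. If the figure served as the expected rate for 1b, an unremarkable number of reactions would look like a large excess. The mQFPD label adds to the worry, because it makes the series read as direct experience with the study product.

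**Working it through.** **Inputs.** All come from Section 14 (mQFPD risk) and are repeated in Section 7: 98 patients; 9 days of treatment; reactions 4 + 2 + 1 = 7; stated incidence 0.07%, with treatment-days as the denominator.

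**Attempt to reproduce the stated figure.**

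- Treatment-days: 98 x 9 = 882.
- Rate per treatment-day: 7 / 882 = 0.00794 = 0.79%.
- Ratio to the stated figure: 0.794 / 0.07 = 11.3. If 0.07 was rounded from anywhere between 0.065 and 0.075, the ratio lies between 10.6 and 12.2.
- Reverse check: 0.0007 x 882 = 0.6 reactions expected, against 7 reported. Seven reactions at 0.07% would need 7 / 0.0007 = 10,000 treatment-days, or about 102 days per patient.

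**Other readings tried.**

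| Variant | Rate |
|---|---|
| 2, 3 or 4 doses a day as denominator | 0.40%, 0.26%, 0.20% |
| 14, 6 or 3 days per patient | 0.51%, 1.19%, 2.38% |
| Only 4 affected patients (full overlap), 882 days | 0.45% |
| 11 events (nausea and vomiting counted separately), 882 days | 1.25% |

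None gives 0.07%. Even the full-overlap reading is more than six times the stated figure (0.4535 / 0.07 = 6.5).

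**Per patient.** If the seven reactions fell in seven different patients, 7 / 98 = 7.1%. If they overlapped as far as possible, 4 / 98 = 4.1%. The documents do not say which. Dividing 7.1% by 0.07% gives 102, but that sets a per-patient figure against one labelled per day. On a common scale, 0.07% a day over 9 days is 0.63% per patient, and 7.14 / 0.63 is again 11.3.

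**Origin.** The proportion 7 / 98 = 0.07 printed with a percent sign would explain the digits. So would a decimal slip in 0.79%, to 0.079%, then truncated. The documents do not settle it.

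**Where the figure is used.** In Section 9, the sample size justification rests on 27 evaluable patients per arm plus dropout and does not mention the rate. The statistical methods summarise safety by treatment group and compare the arms. Section 15 describes daily symptom review, event reporting and regular safety-board calls, with no threshold or expected count tied to a historical rate. Section 18 gives the high mortality of COVID-19 as its reason and points to the background and risk sections as a whole.

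**The case for a change.** The strongest case for a change is that the error is certain and lies in the section where accuracy about harm matters most. It makes a formula with reactions in up to 1 in 14 patients look almost free of them. Carrying the series' daily rate over to 33 patients for 14 days gives 33 x 14 x 7 / 882 = 3.7 expected reactions, against 33 x 14 x 0.0007 = 0.3 on the stated figure. An ethics committee or safety board that relied on the printed rate would start from the wrong expectation.

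The arithmetic stands. The consequences are weaker:

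- No rule in the plan compares 1b with this rate. The comparator is a concurrent placebo arm, which also absorbs symptoms of the disease itself; the background lists nausea among them.
- The expected count of 3.7 is only illustrative. It carries an uncontrolled series at 196 g a day for 9 days over to a trial that the protocol equates to 74.5 g a day for 14 days, with daily diaries.
- The risk is not concealed. Anyone reading the percentage has just read the counts, and the background adds that the series had no control group and was methodologically weak.

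The mQFPD/QFPD mismatch is also real, but it is a matter of wording: the background names the product correctly and Section 14 itself explains the substitution.

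**Conclusion.** The printed 0.07% is wrong on the protocol's own figures. Per treatment-day the counts give 0.79%, about 11 times higher, assuming that all 98 patients completed 9 days and that there were seven reactions. Counting only four affected patients gives 0.45%. The share of patients affected lies between 4.1% and 7.1%, depending on overlap. The understatement is about 11-fold on either scale, not 100-fold.

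This is a clerical slip in a descriptive background figure. Its raw data are printed beside it, and no design quantity, endpoint, test, safety-board procedure or stated conclusion depends on it. Checking the figure against the cited study and tidying the product name belong to proofreading. With the right number in place the trial would be run, monitored and analysed as it is now, so no change to the plan follows.

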#### Brown Rice Placebo Risk

Over the past decade, we at the UCSD Centers for Integrative Health have worked with hundreds of patients with a wide range of disease states including various types of cancer, CAD/CHD, NIDDM, inflammatory bowel disease, and other digestive and autoimmune diseases. In our clinic and several clinical trials we are supporting, we have been offering Medical Nutrition counseling with RD's, diet-focused Integrative Medicine counseling with nutritionally-trained MD's, plant-based cooking classes, dietary coaching, and rigorous nutritional and anthropometric assessments. And on our Integrative Nutrition certificate program, we have been training healthcare professionals in basic nutrition science, clinical nutrition, and the advanced use of food as medicine. In our experience, we have found brown rice, a gluten-free whole grain, to be the single well-tolerated food among our patients. We specifically selected it for the placebo for this reason.

Some have raised hypothetical concerns about problems with grain consumption: (1) gluten exposure, (2) glycemic control in pre-diabetic and diabetic patients, and (3) arsenic contamination. Brown rice: (1) does not contain gluten, (2) tends to improve glycemic control in most individuals (the glycemic index of brown rice is 40% lower than the maltodextrin in a standard "sugar pill"), and (3) poses virtually no risk of arsenic toxicity unless grown in contaminated soils and consumed in large amounts for long periods of time. In the amounts that will be used in this study (24 capsules/day x 500 mg/capsule x 14 days), subjects will be asked to consume just under ½ oz of rice per day - or, to put it in context - the equivalent of one small (6 oz) bowl of brown rice over the course of the study. There is no known risk at this level of consumption.

#### Virulogic risk

According to the WHO, approximately 81% cases of COVID-19 are mild to moderate, and severe disease may require hospitalization in approximately 19% of cases. A total of approximately 5-10% of COVID-19 patients may ultimately require ICU level of care which may include intubation. The CDC estimates the case fatality rate among COVID-19 patients is expected to be between 0.25-3%, with a dramatic increase in death rate among older populations (10 to 27% among persons aged >84 years old). These statistics may change as we learn more about the disease.

#### Reproductive risk:

Given the unknown reproductive risks associated with FoTv, women of childbearing potential (WOCBP) must be willing to use a provided home urine pregnancy test at screening for study entry and excluded from participation if pregnant. All WOCBP must agree to use of contraception throughout the study period and up to 14 days after the last dose of the study medication. It should be noted that there is a current real concern of both teratogenicity from SARS CoV-2 infection itself, as well as increased risk of COVID-19 severe disease for pregnant women. Unfortunately, it is too early in the cycle of the pandemic to know the true risks. As such, pregnant and breastfeeding women will not be recruited for the study.

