## **9. RESEARCH DESIGN AND METHODS**

The following research design applies to each of the following studies:

Sub-study 1a: FoTv vs. placebo for acute COVID-19 patients

Sub-study 1b: QFPD vs. placebo for acute COVID-19 patients

Sub-study 1c: FoTv vs. placebo as an adjunct to COVID-19 vaccination

Sub-studies 1a and 1b of Phase 1 trial will each be 2-arm multicenter double blind randomized placebo controlled clinical trials.

Each of these safety/feasibility sub-studies will be conducted identically with the exception of additional exclusion criteria that will be required for sub-study 1b on account of the presence of herbal components including ephedrine that require these precautions for avoiding herb-drug interactions.

Sub-study 1c will be a single site double blind randomized placebo controlled clinical trial.

This will be a shorter intervention with broader inclusion criteria.

The research design and methods for the larger efficacy trial (Phase 2) will require analysis of these first two feasibility studies, and the final protocol will be submitted as a future amendment.

The primary objective of sub-studies 1a and 1b will be to assess the safety of FoTv or mQFPD, respectively, when used as therapies for acute COVID-19 infection and feasibility of the study protocol.

The primary objectives of sub-study 1c will be to ascertain the safety of FoTv when used as an adjunct to standard COVID vaccination as well as to evaluate its effects on post-vaccine COVID-19 antibody titers and on vaccination-related side effects.

A total of 66 subjects (33 FoTv or mQFPD and 33 placebo) will be enrolled in each of the 1a and 1b sub-studies.

A total of 266 subjects (133 FoTv and 133 placebo) will be enrolled in sub-study 1c.

The study protocol will be implemented and safety, feasibility, clinical, and laboratory data will be collected.

Interested participants will be asked to contact the study team, who will then conduct screening, consenting, and study enrollment. The study will be open to patients who are

- a) Mildly-to-moderately symptomatic and have tested positive for COVID-19 (sub-studies 1a and 1b)
- b) Scheduled for COVID-19 vaccination (sub-study 1c).

See section 11 for recruitment plan.

Once their eligibility has been confirmed, participants will be randomized to one of two groups by the study statistician:

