- Group 1 – either Mycelium of *Fomitopsis officinalis* and *Trametes versicolor* (FoTv) for sub-studies 1a and 1c or modified Qing Fei Pai Du Tang (mQFPD) for sub-study 1b
- Group 2 - Inert placebo (encapsulated brown rice)

We anticipate screening approximately 90 or 75 potential candidates per sub-study in order to consent and enroll 66 or 48 participants to account for up to 20% drop-out rate.

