#### **(2) End-of-Treatment:**

For patients who are not hospitalized, the study phlebotomist will collect their specimens at Day 14 for the following laboratory tests:

- Basic Metabolic Panel
- Complete Blood Count with Differential
- Liver Function Testing

- Prothrombin Time and Partial Thromboplastin Time
- Ferritin
- D-Dimer
- Lactate Dehydrogenase
- C-Reactive Protein
- Troponin
- T-cell differentiation panel
- Salivary or nasal swab samples will be collected for SARS CoV-2 viral load assays
- Plasma, serum, and whole blood will be collected and banked for cytokine, immunological, and metabolomic assays

For subjects who require hospitalization by Day 14, results of the following laboratory tests will be obtained from their hospital records (please note that these tests are routinely conducted as part of COVID-19 treatment and results should be available within subjects' medical records):

- Admission Basic Metabolic Panel,
- Complete Blood Count with Differential, and
- Liver Function Testing.

Please note that medical records will also be reviewed for SARS-CoV-2 viral load, any inflammatory biomarkers (CRP, procalcitonin, IL-6, ferritin, D-dimer, lactate dehydrogenase) as well as markers of myocarditis (troponin, CK-MB) and further lymphocyte differentiation (T-Cell differentiation panel).

Sub-study 1c:

Sample collection will occur at the following time points:

- Single dose vaccine (such as J&J): baseline, day 14, day 28, and 6 months post vaccination
- Two-dose vaccine (such as Pfizer or Moderna): baseline, day 14, two weeks after your second dose, and 6 months post vaccination
- Vaccine booster: baseline, day 3, day 14, and 6 months

For all time points:

The following test will be run to establish values of immunogenicity against SARS CoV-2:

- SARS CoV-2 IgG antibody titer
- Cytokines and T-cell assays

For time points Baseline and Day 14:

The following laboratory assays will be conducted to ascertain FoTv safety:

- Basic Metabolic Panel
- Liver Function Tests

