### Test Product Dose and Route of Administration

Participants in sub-studies 1a and 1b: The dosage of FoTv or mQFPD is 8 capsules three times a day for 14 consecutive days. It does not need to be consumed with food. It is best taken at least 30 minutes before OR at least 60 minutes after meals, in the morning, noon and evening. Accidentally missed doses will not need to be taken at a later time, but will be recorded in a daily diary. Should swallowing capsules be an issue, they can be opened and dispensed into water or juice for easy ingestion.

Participants in sub-study 1c: The dosage of FoTv is 8 capsules three times a day for 4 consecutive days ((starting with the day of the first vaccination). It does not need to be consumed with food. It is best taken at least 30 minutes before OR at least 60 minutes after meals, in the morning, noon and evening. Accidentally missed doses will not need to be taken at a later time, but

will be recorded in a daily diary. Should swallowing capsules be an issue, they can be opened and dispensed into water or juice for easy ingestion

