#### **Inclusion Criteria**

1. Scheduled to receive COVID-19 vaccination
2. Age 18 and older

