#### **Exclusion Criteria**

1. Current use of investigational agents to prevent or treat COVID-19
2. Prisoners
3. Known liver disease
4. Known renal disease or acute nephritis.
5. Pregnant or breastfeeding women
6. Use of immunosuppressive medication

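### Sub-study 1c's eligibility criteria omit the pregnancy test and contraception agreement that section 14 requires because FoTv's reproductive risk is unknown

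*Combined protocol and SAP*

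**What the plan says.** Section 14, under Reproductive risk, starts from the unknown reproductive risk of FoTv. It says that women of childbearing potential "must be willing to use a provided home urine pregnancy test at screening for study entry", and then: "All WOCBP must agree to use of contraception throughout the study period and up to 14 days after the last dose". No sub-study is named or exempted.

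Section 9 assigns FoTv as the active product in two of the three sub-studies: "FoTv) for sub-studies 1a and 1c or modified Qing Fei Pai Du Tang (mQFPD) for sub-study 1b". For 1c, Test Product Dose and Route of Administration states: "The dosage of FoTv is 8 capsules three times a day for 4 consecutive days". The daily dose in 1a is the same, taken for 14 days.

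Section 10 gives 1c two inclusion criteria. One is "Scheduled to receive COVID-19 vaccination"; the other is an age of at least 18. The relevant 1c exclusion reads "Pregnant or breastfeeding women". Section 9, Medical History, has pregnancy and lactation status recorded at screening. The section 9 design text says of 1c: "This will be a shorter intervention with broader inclusion criteria".

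Inclusion criterion 3 of both 1a and 1b requires a negative pregnancy test and agreement to contraception for the study period. Their package contains a urine test, and the result is to be self-reported before study medication is started.

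**The concern.** Section 14 makes the test a condition of entry, but a woman of childbearing potential can satisfy every 1c criterion in section 10 without taking it or agreeing to contraception. Staff who screen from section 10 would not be prompted to ask for either.

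What is at stake is narrow. An exclusion that rests on reported status catches pregnancies the woman knows about. It does not catch a pregnancy unrecognised at the first dose, and it does nothing about one that begins around the dosing days. These are the cases that a test and a contraception agreement address. Elsewhere in the protocol the exclusion is not treated as enough by itself: 1a and 1b exclude pregnant and breastfeeding women and still add both safeguards.

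**Working it through.** No sample size, power or error rate depends on this point, so the main check is a comparison of texts. A little arithmetic then gives the scale.

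**Comparison of the section 14 rule with the sub-studies**

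| Element | 1a and 1b | 1c |
|---|---|---|
| Pregnant or breastfeeding women excluded (section 10) | Yes | Yes |
| Status recorded at screening (section 9, Medical History) | Yes | Yes |
| Negative test as an inclusion criterion (section 10) | Yes, criterion 3 | No |
| Contraception agreement as an inclusion criterion (section 10) | Yes, criterion 3 | No |
| Test kit in the package (section 9) | Yes | Not listed in the readable text; one bullet is blank |
| Result required before dosing (section 9, Baseline) | Yes | Not stated |

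The third and fourth rows carry the finding. The 1c criteria are fully readable and contain neither item.

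**Does section 14 reach 1c?** Its stated ground is FoTv, which 1c gives. The contraception sentence covers all women of childbearing potential. The remarks on SARS-CoV-2 infection in pregnancy come afterwards and are not the ground given for the test. The section 9 remark about broader criteria mentions neither pregnancy testing nor contraception, so it cannot be taken as an exemption.

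**Exposure** (section 9, dosing)
- Daily dose in 1a and in 1c: 8 × 3 = 24 capsules.
- Course in 1c: 24 × 4 = 96 capsules.
- Course in 1a: 24 × 14 = 336 capsules.
- Ratio: 96 / 336 = 0.286, about 29%.

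**Women covered by the rule in 1c.** Section 9 gives 266 subjects, 133 per arm. The share of women of childbearing potential is not given, so 10% to 40% is assumed.
- All of 1c: 0.10 × 266 = 26.6 to 0.40 × 266 = 106.4, that is 27 to 106.
- FoTv arm: 0.10 × 133 = 13.3 to 0.40 × 133 = 53.2, that is 13 to 53.

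These figures count women to whom the rule applies, not pregnancies. The number of unrecognised pregnancies would be a small part of them and cannot be derived from the documents.

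**Contraception window in 1c.** Section 14 joins two end points, the study period and 14 days after the last dose. Dosing plus 14 days is 4 + 14 = 18 days, whereas 1c follow-up contacts run to 12 months after baseline. The wording does not settle which applies to 1c.

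**The case against.** The strongest reply is that the rule already exists. Section 14 is not limited by sub-study, so it can be read as binding 1c whatever section 10 repeats. That is a fair reading, and it makes this an inconsistency between two sections rather than a missing policy. It does not remove the point: on that reading section 14 bars women whom section 10 admits.

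A reader might infer more than the documents support, in five ways.

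- *That 1c admits pregnant women.* It does not. They are excluded and status is recorded at screening.
- *That the plan provides no kit and no contraception agreement for 1c at all.* This is not shown. The blank bullet in the 1c package list sits between the medication and the written instructions, where the 1a/1b list has the thermometer and the pregnancy test; it may be a lost item or a deleted one. Consent pages were not available and may record an agreement. Neither possibility changes what the 1c criteria say.
- *That the 1c laboratory list proves the omission.* The list introduced by "The following laboratory assays will be conducted to ascertain FoTv safety" holds a metabolic panel and liver tests at baseline and day 14. A self-reported home test is an entry check and need not appear in a list of repeated safety assays, so its absence there is weak evidence.
- *That 1a and 1b are a clean model.* They are not. Their criterion 3 accepts urine or serum and then asks for serum, no serum test is on their laboratory schedule, and the kit ships after enrolment although section 14 places the test at screening. The comparison shows only that their criteria contain both requirements.
- *That section 14 should be read everywhere as dosing plus 14 days.* In 1a and 1b that would be 14 + 14 = 28 days, while their criteria require contraception throughout the study period and participation runs to about day 58. Such a reading would cut an existing safeguard by roughly half.

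**Conclusion.** The point holds as an internal inconsistency of minor to moderate weight, concerning participant safety. Section 14 requires a screening pregnancy test and a contraception agreement on account of FoTv; the 1c eligibility criteria contain neither, although 1c gives FoTv at the daily dose used in 1a.

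The size is modest. Known pregnancies are excluded, the 1c course is 29% of the 1a course, and no endpoint or analysis is affected. The range of 27 to 106 women covered, 13 to 53 of them on FoTv, rests wholly on the assumed 10% to 40% share. The conclusion itself rests on reading section 14 as applying to every sub-study that gives FoTv, which its wording supports and nothing in the documents contradicts.

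**What to change.** Add one inclusion criterion to 1c in section 10: women of childbearing potential must have a negative home urine pregnancy test at screening, before the first dose, and must agree to use contraception during dosing and for at least 14 days after the last dose.

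List the test among the 1c screening procedures in section 9 and, if it is not already there, put the kit in the 1c package. The package goes out after enrolment, so the kit may have to be sent ahead of it for the test to be done at screening; in any case no capsule should be taken until a negative result is reported.

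State the 1c contraception window explicitly. Dosing plus 14 days gives a minimum of 18 days; if the sponsor intends the full 12 months, the text should say so. Leave the 1a and 1b requirement as it stands.

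The cost is one home kit per woman of childbearing potential (27 to 106 under the assumed share), slightly narrower 1c eligibility, and a short wording change. The kit and the self-report procedure already exist for 1a and 1b.
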